**NOTES:**

- AEs that occur or worsen during interruptions of randomized study treatment will be classified as treatment emergent and post-randomization.
- If the last non-zero dose date is missing and the treatment start date is non-missing and the AE onset date or AE worsening date is on or after the treatment start date, then the AE will be considered to be treatment emergent.
- If AE onset date or AE worsening date is missing and AE resolution date is before the treatment start date, then the AE will be classified as Pre-treatment.
- If AE onset date or AE worsening date is missing and AE resolution date is either missing or on or after treatment start date, then the AE will be classified as treatment emergent and post-randomization.

#### 14.4.1.5. Study Phases for Concomitant Medication (Other Than IV Iron Dose Endpoints and Iron Use Summaries)

Pre-treatment medications are those taken (i.e., started) before the start date of study treatment. On-treatment medications are those taken (i.e., started or continued) at any time between the study treatment start date and the last non-zero dose date + 1 day, inclusive. Pre-treatment medications that were continued during this on-treatment period are also considered to be on-treatment medications. Post-treatment medications are those taken (i.e., started or continued) at any time after the last non-zero dose date + 1 day. On-treatment medications that were continued during this post-treatment period are also considered to be post-treatment medications. Post-randomization medications are those taken (i.e., started or continued) at any time on or after the randomization date.

It will be assumed that the medication has been taken on the date in which it is reported as started or stopped. Also, for any medication starting on the same date as study treatment, it will be assumed that the medication was taken after the subject started taking study treatment.

CONFIDENTIAL

204837

Illustrations of the pre-treatment, on-treatment, and post-treatment treatment states are included below:

	Pre-treatment	On-treatment			Post-treatment	Pre-treatment medication	On-treatment medication	Post-treatment medication
		Randomized Treatment Start Date	Last Non-zero Dose Date + 1 Day	Last Non-zero Dose Date + 2 Days				
(a)	x—x					Y	N	N
(b)	x—		—x			Y	Y	N
(c)	x—				—x	Y	Y	Y
(d)		x—x				N	Y	N
(e)		x—			—x	N	Y	Y
(f)					x—x	N	N	Y
(g)	?—x					Y	N	N
(h)	?—		—x			Y*	Y	N
(i)	?—				—x	Y*	Y*	Y
(j)	x—				—?	Y	Y**	Y**
(k)		x—			—?	N	Y	Y**
(l)					x—?	N	N	Y
(m)	?—				—?	Y***	Y***	Y***
(n)	x—	x				Y	Y	N
(o)	?—	x				Y*	Y	N
(p)		x	—x			N	Y	N
(q)		x		x		N	Y	N
(r)				x	—x	N	Y	Y
(s)				x	—?	N	Y	Y**
(t)				x	—x	N	N	Y
(u)				x	—?	N	N	Y
(v)		x—		—	x	N	Y	Y

x = start/stop date of medication

? = missing start/stop date of medication

\* If a medication is stopped On-treatment or Post-treatment and no start date is recorded it will be assumed that the medication was ongoing from the Pre-treatment phase

\*\* If a medication is started Pre-treatment or On-treatment and no stop date is recorded then usage will be assumed to be ongoing for the remainder of the study

\*\*\* If a medication has no start or stop date it will be assumed that the medication was ongoing from the Pre-treatment phase to the Post-treatment phase

## 14.5. Appendix 5: Data Display Standards & Handling Conventions

### 14.5.1. Reporting Process

Software	

 
The currently supported versions of SAS software will be used.
 
	
Reporting Area	
HARP Server	: uk1salx00175
HARP Compound	: gsk1278863/mid204837
Analysis Datasets	

 
Analysis datasets will be created according to CDISC standards (SDTM IG Version 3.2 & ADaM IG Version 1.1).
 
For creation of ADaM datasets (ADCM/ADAE), the same version of dictionary datasets will be implemented for conversion from system independent (SI) to SDTM
 
	
Generation of RTF Files	

 
RTF files will be generated for Tables
 
	

### 14.5.2. Reporting Standards

General

 
The current GSK Integrated Data Standards Library (IDSL) will be applied for reporting, unless otherwise stated (IDSL Standards Location: https://spope.gsk.com/sites/IDSLLibrary/SitePages/Home.aspx):             
 
4.03 to 4.23: General Principles
 
5.01 to 5.08: Principles Related to Data Listings
 
6.01 to 6.11: Principles Related to Summary Tables
 
7.01 to 7.13: Principles Related to Graphics
 
 
 
Do not include subject level listings in the main body of the GSK Clinical Study Report. All subject level listings should be located in the modular appendices as ICH or non-ICH listings
 
In all displays (TFLs) the term "Subjects", which reflects CDISC and GSK Data Display Standards terminology, will be used to refer to the "Participants". In this Reporting and Analysis Plan, "subject" and "participant" are used interchangeably.
 

Formats

 
GSK IDSL Statistical Principles (5.03 & 6.06.3) for decimal places (DP's) will be adopted for reporting of data based on the raw data collected, unless otherwise stated.
 
Numeric data will be reported at the precision collected on the eCRF.
 
The reported precision from non eCRF sources will follow the IDSL statistical principles but may be adjusted to a clinically interpretable number of DP's.
 

Planned and Actual Time

 
Reporting for tables, figures and formal statistical analyses:             
 
Planned time relative to randomization will be used in figures, summaries, statistical analyses and calculation of any derived parameters, unless otherwise stated.
 
All scheduled visits, regardless of deviation from the planned assessment times and/or scheduled visit days, will be used in tables, figures and formal statistical analyses unless otherwise stated.
 
 
 

**CONFIDENTIAL**

204837

 
The derived end of treatment value (see Section 14.6.1) will also be included in displays of data by visit.
 
Tables presenting data values by visit will also include values from scheduled visits occurring on or before the Day 1 visit, despite the description contained in the title (e.g., post-randomization, evaluable, or on-treatment). The description in the title refers to the post-randomization values that are included in the table.
 
For the purpose of statistical summary and analysis, unless otherwise specified, the data for visits after discontinuation of study treatment recorded under Early Trt Disc Wk xx visit will be summarized and analyzed along with the corresponding Wk xx visits for subjects who complete the study treatment.
 
Reporting for Data Listings: 
 
Planned and actual time relative to study drug dosing will be shown in listings (Refer to IDSL Statistical Principle 5.05.1).
 
Unscheduled or unplanned readings will be presented within the subject's listings.
 
Visits outside the protocol defined time-windows (i.e. recorded as protocol deviations) will be included in listings.
 
 
 
	
Unscheduled Visits	

 
Unscheduled visits will not be included in summary tables, with the following exceptions: 
 
If the table includes a row for all post-baseline assessments, unscheduled visits will be included in this row.
 
Some Hgb endpoints will include unscheduled Hgb values (See Section 14.6.3)
 
Some BP endpoints will include unscheduled BP values (see Section 14.6.4)
 
 
 
Unscheduled visits will not be included in figures, with similar exceptions: 
 
If the figure includes a data value for all post-baseline assessments, unscheduled visits will be included in this value.
 
Some Hgb endpoints will include unscheduled Hgb values (See Section 14.6.3)
 
Some BP endpoints will include unscheduled BP values (see Section 14.6.4)
 
 
 
All unscheduled visits will be included in listings.
 
	
Descriptive Summary Statistics	
Continuous Data	Refer to IDSL Statistical Principle 6.06.1
Categorical Data	N, n, frequency, %
Graphical Displays	

 
Refer to IDSL Statistical Principals 7.01 to 7.13.
 
	

**14.5.3. Reporting Standards for Pharmacokinetic**

Pharmacokinetic Concentration Data	
Descriptive Summary Statistics, Graphical Displays and Listings	Refer to IDSL PK Display Standards. Refer to IDSL Statistical Principle 6.06.1. Note: Concentration values will be imputed as per GUI_51487 v5.0 for descriptive summary statistics/analysis and summarized graphical displays only. Note: PC WNL file or NONMEM/Pop PK is Not applicable for Non-compartmental analysis.
Pharmacokinetic Parameter Derivation	
PK Parameter to be Derived by Programmer	The following PK parameters will be derived by the Clinical Programmer: Ctrough, Cmax, tmax Formulas for these derivations are given in Section 14.6.5.

**CONFIDENTIAL**

204837

Pharmacokinetic Parameter Data	
Is NQ impacted PK Parameters Rule Being Followed	No.
Descriptive Summary Statistics, Graphical Displays and Listings	Refer to IDSL PK Display Standards.

## 14.6. Appendix 6: Derived and Transformed Data

### 14.6.1. General

Multiple Measurements at One Time Point
 
 
• Mean of the measurements will be calculated and used in any derivation of summary statistics but if listed, all data will be presented. 
 
○ Triplicate BP and HR measurements are expected at certain time points (See Section 14.2.1)
 
 
 
• Subjects having both High and Low values for Normal Ranges at any post-baseline visits for safety parameters will be counted in both the High and Low categories of “Any visit post-baseline” row of related summary tables. This will also be applicable to relevant Potential Clinical Importance summary tables.
 

Randomization Date
 
 
• Date subject was randomized
 

Treatment Start Date
 
 
• First randomized treatment dose start date
 

Last Non-Zero Dose Date
 
 
• Date of last actual dose of active study treatment from the eCRF Study Treatment/Compliance Record Form. 
 
○ The dose steps used by the dosing algorithm described in the protocol include a dose hold or a zero dose. If subjects are assigned by the algorithm to a zero dose, they only receive placebo and saline, and do not receive active study treatment for that period. When a dose interruption is required, both active treatment and placebo/saline will be interrupted. Hence, it would be possible for a subject to complete the study, while still following the dosing algorithm, but not actually taking any active study treatment. The last non-zero dose date, then captures the latest date in the study that a subject physically took a dose of active study treatment.
 
 
 

Treatment Stop Date
 
 
• Calculated as the latest study treatment dose stop date, after excluding the records for missed dose.
 


End of Treatment Value
 
 
• Only defined for subjects with a non-missing treatment start date
 
• Hgb, iron, transfusion and PRO parameter: the latest value on or before the treatment stop date + 1 day.
 
• Blood pressure, central laboratory, and vital signs parameters: the latest value on or before the last non-zero dose date + 1 day.
 

CONFIDENTIAL

204837

Study Completion/Withdrawal Date

 
Date of withdrawal for subjects withdrawing (i.e., subjects who actively withdraw or are deemed lost to follow-up) from study or date of completion of study for subjects who complete the study. 
 
Note: Subjects who die while on study are considered as having completed the study
 
 
 

Planned/Actual Visit Dates

 
Planned/actual visit dates will be defined as follows: 
 
Week 28 date: Non-missing Week 28 visit start date (from SV domain), otherwise randomization date + 28*7
 
Week 36 date: Non-missing Week 36 visit end date (from SV domain), otherwise randomization date + 36*7
 
Week 52 date: Non-missing Week 52 visit end date (from SV domain), otherwise randomization date + 52*7
 
 
 

Stabilization Period
Defined as the period between and including the randomization date + 1 day - <Week 28 visit, using planned/actual dates.
Alternative Evaluation Period (Alt. EP)
Defined as the period between and including Week 28 visit – Week 36 visit, using planned/actual dates.
Evaluation Period (EP)
Defined as the period between and including Week 28 visit – Week 52 visit, using planned/actual dates.
Study Day

 
Calculated as the number of days from randomization date: 
 
Ref Date = Missing → Study Day = Missing
 
Ref Date < Randomization Date → Study Day = Ref Date – Randomization Date
 
Ref Date ≥ Randomization Date → Study Day = Ref Date – (Randomization Date) + 1
 
 
 

Treatment Day

 
Calculated as the number of days from treatment start date: 
 
Treatment Start Date = Missing → Treatment Day = Missing
 
Ref Date < Treatment Start Date → Treatment Day = Ref Date – Treatment Start Date
 
Ref Date ≥ Treatment Start Date → Treatment Day = Ref Date – (Treatment Start Date) + 1
 
 
 

Last Study Contact Date

 
Latest visit date from an unscheduled visit or a clinic, telephone, designated third party, healthcare provider or medical records, or other contact with subject (mail, email, text, social media, etc.) visit.
 

Time Definitions (per GSK standard principles)

 
1 week = 7 days
 
1 month = 30.4375 days
 
1 year = 365.25 days
 

Production of Two-Sided p-values

 
The majority of the efficacy and safety analyses in this study will use one-sided 2.5% p-values assess statistical significance. Should two-sided p-values be required for publication purposes after the study is complete, the corresponding two-sided p-values will be produced at that time.
 

CONFIDENTIAL

204837

## 14.6.2. Study Population

### 14.6.2.1. Demographics & Baseline Characteristics

Demographics & Baseline Characteristics
Age

 
• GSK standard IDSL algorithms will be used for calculating age where birth date will be imputed as follows:               
 
○ Any subject with a missing day will have this imputed as day '15'.
 
○ Any subject with a missing date and month will have this imputed as '30th June'.
 
 
 
• Birth date will be presented in listings as 'YYYY'.
 

High Level Race

 
• Geographic ancestry data will be combined into five high level race categories:               
 
○ American Indian or Alaskan Native
 
○ Asian (Asian-East Asian Heritage, Asian-Japanese Heritage, Asian-Central/South Asian Heritage, Asian-South East Asian Heritage, Mixed Asian Race)
 
○ Black or African American
 
○ Native Hawaiian or Other Pacific Islander
 
○ White (White-Arabic/North African Heritage, White-White/Caucasian/European Heritage, Mixed White Race)
 
○ Mixed Race (Multiple high level races are selected)
 
 
 
 
Note: A subject will only be counted in one category. Mixed Asian Race includes subjects who have more than one Asian category selected, but no other categories. Mixed White Race includes subjects who have more than one White category selected, but no other categories.

Race Detail

 
• Geographic ancestry data will be combined into race detail categories:               
 
○ American Indian or Alaskan Native
 
○ Asian-Central/South Asian Heritage
 
○ Asian-East Asian Heritage
 
○ Asian-Japanese Heritage
 
○ Asian-South East Asian Heritage
 
○ Mixed Asian Race
 
○ Black or African American (African American/African Heritage)
 
○ Native Hawaiian or Other Pacific Islander
 
○ White-Arabic/North African Heritage
 
○ White-White/Caucasian/European Heritage
 
○ Mixed White Race
 
○ Mixed Race (Multiple high level races are selected)
 
 
 
 
Note: A subject will only be counted in one category. Mixed Asian Race includes subjects who have more than one Asian category selected, but no other categories. Mixed White Race includes subjects who have more than one White category selected, but no other categories.

Prior ESA Type and Standardized Prior ESA Dose (U/week) at Randomization

 
• During the screening period, subjects may be receiving ESAs in multiple ways, including: epoetin IV or SC, darbepoetin IV or SC, or methoxy PEG-epoetin beta IV or SC.
 
• A subject's prior ESA type will be determined from the records that contribute to the subject's standardized prior ESA dose. The following categories of prior ESA type will be summarized:
 

**CONFIDENTIAL**

204837

**Demographics & Baseline Characteristics**

- Darbepoetin alfa only
  - Epoetin only
    - This group contains subjects using any of the following types of epoetin: epoetin alfa, epoetin beta, epoetin lambda, epoetin theta, and epoetin zeta.
  - Methoxy PEG-epoetin beta only
    - This group contains subjects using methoxy PEG-epoetin beta and pegzerepoetin alfa.
  - Multiple
    - This group contains subjects using any combination of the ESA types.
  - Missing
- The dose of ESA will be standardized to obtain a continuous single unit prior ESA dose in terms of epoetin IV U/week for the period from the Week -4 visit to the day before the Randomization date.
  - All prior ESA therapy concomitant medication records from screening will be selected and ordered by start date and end date.
  - The standardization will be carried with the following formula:
  - For subjects taking epoetin IV:
    - Standardized ESA dose (U/week) = epoetin IV dose (U)\*frequency
  - For subjects taking epoetin SC:
    - Standardized ESA dose (U/week) = (161/113)\*epoetin SC dose(units)\*frequency
  - For subjects taking darbepoetin IV or SC:
    - Standardized ESA dose (U/week) = 250\* darbepoetin dose (μg)\*frequency
  - For subjects taking methoxy PEG-epoetin beta:
    - Standardized ESA dose (U/week) = 208\*methoxy PEG-epoetin beta dose (μg)\*frequency

Note: Frequency and Gap Factors defined as follows:

Frequency (from eCRF)	Frequency (for standardization formula)	Gap Factor
One time dose	see below	n/a
Four times per week	4	0.75 day
Three times per week	3	1.33 days
Two times per week	2	2.5 days
Every week	1	6 days
Every 10 days	0.70	9 days
Every 2 weeks	0.50	13 days
Every 3 weeks	0.33	20 days
Every 4 weeks	0.25	27 days
Every 5 weeks	0.20	34 days
Every 6 weeks	0.167	41 days
Every 8 weeks	0.125	55 days

- If the frequency of the record is not 'one time dose', then duration is calculated as follows:

CONFIDENTIAL

204837

**Demographics & Baseline Characteristics**

- If the concomitant medication record start date  $\geq$  Randomization date, the duration of the record is 0.
- If the concomitant medication record end date + gap factor  $<$  Week -4 visit date, the duration of the record is 0.
- If the concomitant medication record end date + gap factor  $\geq$  Week -4 visit date, the duration of a record will be calculated as Stop Date – Start Date +1 day, where:
  - Start date will be the latest of (concomitant medication record start date and the Week -4 visit date).
  - Stop date will be the concomitant medication record end date + gap factor.
- If the frequency of the record is 'one time dose', then:
  - If the concomitant medication record start date  $\geq$  Randomization date, the duration of the record is 0.
  - If Week -4 visit date  $\leq$  concomitant medication record start date, then:
    - Frequency (for standardization formula) = 1
    - Duration = 7 days
  - If concomitant medication record start date  $<$  Week -4 visit date, then:
    - Frequency (for standardization formula): 7/ [earliest of (the day before the next sequential prior ESA concomitant medication record start date and the day before randomization) – start date of record + 1 day]
    - If the earliest non-missing date of (the day before the next sequential prior ESA concomitant medication record start date and the day before randomization)  $<$  Week -4 visit date, the duration of the record is 0.
    - If the earliest non-missing date of (the day before the next sequential prior ESA concomitant medication record start date and the day before randomization)  $\geq$  Week -4 visit date, the duration of the record is calculated as Stop Date – Start Date + 1, where:
      - Start date will be the Week -4 visit date.
      - Stop date will be the earliest of (the day before the next sequential prior ESA concomitant medication record start date and the day before randomization)
- The total dose for each prior ESA record will be: Standardized dose\*duration/7days
- A weighted mean will then be used to obtain the prior ESA dose:  
 Mean prior ESA dose = [(ESA total doseRecord 1) + ... + (ESA total doseRecord n)]/[( Randomization Date – Week -4 Visit Date)/7days]

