6.1. Inclusion Criteria

Participants are eligible to be included in the study only if all of the following criteria apply at **screening (Week -4)** and **randomization (Day 1)**, unless otherwise specified:

1. **Age:** Participant must be 18 to 99 years of age inclusive, at the time of signing the informed consent.

Note: Country-specific age requirements for Korea are provided in [Appendix 8](#), Section 12.8.2.

2. **RhEPO or its analogs:** Use of any approved rhEPO or analog for at least 8 weeks prior to the screening visit and continuing during the screening period until randomization (Day 1).
3. **Hemoglobin** concentration (measured by HemoCue) within the following range:

	Hgb Range (inclusive)
Week -4	
 • Hgb 8 to 11.5 g/dL¹ (5 to 7.1 mmol/L). • If Hgb is 11.6 to 11.9 g/dL² (7.2 to 7.4 mmol/L), up to two retests are allowed; the retest value must be between 8 to 11.5 g/dL¹ (5 to 7.1 mmol/L).
Day 1	
 • Hgb 8 to 11 g/dL¹ (5 to 6.8 mmol/L) and receiving at least the minimum rhEPO or analog dose³. • Hgb >11 to 11.5 g/dL¹ (6.8 to 7.1 mmol/L) and receiving greater than the minimum rhEPO or analog dose³.

1. Conversion from g/dL to g/L is 1:10, e.g., Hgb of 8 to 10 g/dL is equivalent to 80 to 100 g/L.
2. The first retest will use the original Week -4 blood sample. If the retest value is >11.5 g/dL, one additional retest can be performed using a new blood sample on the study visit day. The **final** retest value is entered into the IRT system. Retests will be done prior to dialysis.
3. **Minimum rhEPO or analog dose:** Epoetins (including biosimilars): 1500 units (U)/week intravenous (IV) or 1000 U/week subcutaneous (SC); Darbepoetin alfa: 20 µg/4 weeks SC/IV; Methoxy PEG-Epoetin: 30 µg/month SC/IV.

4. **Dialysis:** On hemodialysis (including hemofiltration or hemodiafiltration) >90 days prior to screening and continuing during the screening period.
5. **Frequency of Dialysis:** On hemodialysis (in-center) ≥ 3 times per week.
6. **Sex:** Male and female participants are eligible. A female participant is eligible to participate if she is not pregnant (see [Appendix 4](#)), not breastfeeding, and at least one of the following conditions applies:
 - Not a woman of childbearing potential (WOCBP) as defined in [Appendix 4](#), or

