**Baseline Erythropoietin Resistance Index (ERI, U/kg/wk/g/L)**

- Calculated by dividing the standardized prior ESA dose (U/week) at randomization by the baseline estimated dry weight (in kg) and then dividing by the achieved Day 1 Hgb (in g/L).
- Note: the central laboratory Hgb value from Day 1 should be used to calculate ERI, however if this value is missing and there is a corresponding non-missing HemoCue Hgb value available, the Day 1 HemoCue Hgb value will be used.

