**Standardized Baseline IV Iron Dose (mg/month)**

- In order to calculate the baseline average monthly IV iron dose, the dose of IV iron will be standardized to obtain a continuous single unit IV iron dose in terms of mg/month for the period from 12 weeks before the Randomization date to the day before the Randomization date.
- IV iron therapy concomitant medication records that occur or are ongoing during the period from (the Randomization date – 12 weeks) to the day before the Randomization date will be selected and ordered by start and end date.
- The standardization will be carried out with the following formula:
  - Standardized IV iron dose (mg/week) = IV iron drug dose (mg) \* frequency

Note: Frequency and Gap Factors defined as follows:

Frequency (from eCRF)	Frequency (for standardization formula)	Gap Factor
2 times per week	2	2.5 days
3 times per week	3	1.33 days
4 times per week	4	0.75 day
5 times per week	5	0.4 day
BID	14	0 days
Once daily	7	0 days
One time dose	1	n/a
Every 12 Hours	14	0 days
Every 2 weeks	0.5	13 days
Every 4 weeks	0.25	27 days
Once a month	0.23	29 days
Once a week	1	6 days
TID	21	0 days

- If the frequency of the record is not 'one time dose', then duration is calculated as follows:
  - If the concomitant medication record start date  $\geq$  Randomization date, the duration of the record is 0.
  - If the concomitant medication record end date + gap factor  $<$  (Randomization date – 12 weeks), the duration of the record is 0.
  - If the concomitant medication record end date + gap factor  $\geq$  (Randomization date – 12 weeks) or the record is ongoing, the duration of the record will be calculated as Stop Date – Start Date + 1 day where:
    - Start date will be the latest of (concomitant medication record start date and the (the Randomization date – 12 weeks)).
    - Stop date will be the earliest of (concomitant medication record stop date + gap factor and the day before randomization).
- If the frequency of the record is 'one time dose', then:

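### The prior ESA dose rule lets repeating records run past randomization, inflating the dose and ERI when a record ends less than one dosing interval before Day 1

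*SAP*

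**What the plan says.** SAP 14.6.2.1 (Prior ESA Type and Standardized Prior ESA Dose) converts each ESA record to IV epoetin units per week "for the period from the Week -4 visit to the day before the Randomization date". Each record contributes as follows: "The total dose for each prior ESA record will be: Standardized dose\*duration/7days". The sum is then divided by the length of the window in weeks, "Randomization Date – Week -4 Visit Date)/7days".

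For any record that is not a one-time dose, the start date is truncated at the Week -4 visit, but the end is not truncated: "Stop date will be the concomitant medication record end date + gap factor".

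Two neighbouring rules do stop at randomization. For a one-time ESA dose given before Week -4, "Stop date will be the earliest of (the day before the next sequential prior ESA concomitant medication record start date and the day before randomization". For baseline IV iron (SAP 14.6.3.2), "Stop date will be the earliest of (concomitant medication record stop date + gap factor and the day before randomization".

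The resulting dose feeds the split at 7,000 U/week (SAP 5.4.2) and ERI: "Calculated by dividing the standardized prior ESA dose (U/week) at randomization by the baseline estimated dry weight (in kg", and then by Day 1 Hgb. A participant is a hyporesponder at ERI ≥2.0 U/kg/wk/g/L or at ≥450 U/kg/week.

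**The concern.** The numerator can include days after randomization that the denominator never includes. The contribution of a record is linear in its duration, so each extra day raises the mean weekly dose in proportion, and ERI with it.

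The possible error grows with the dosing interval because the gap factor does: 1.33 days for three-times-weekly dosing, 27 days for 4-weekly and 55 days for 8-weekly. Misclassification would therefore follow prior ESA product and schedule. The hyporesponder and ≥7,000 U/week groups could take in some participants because they were dosed at long intervals, not because they needed a high dose.

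Hyporesponder status is used in the baseline tables (SAP 6.2.4), in subgroup analyses of the primary endpoint with nominal non-inferiority and superiority p-values (5.4.2), and in the Hgb variability, time to rescue, transfusion and dose adjustment displays (7.3.1, 7.4.1).

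**Working it through.** The documents give no figure to reproduce, so the check works through the rule itself.

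**Inputs.**
- W is the number of days from the Week -4 visit to randomization: 28 if nominal (4-week screening).
- g is the gap factor from the SAP 14.6.2.1 table. Within rounding it equals the dosing interval minus one day: 7/3 − 1 = 1.33 for three times weekly, 7 − 1 = 6 for weekly, 28 − 1 = 27 for 4-weekly, 56 − 1 = 55 for 8-weekly.
- The record is assumed to start on or before Week -4 and to be the only record in the window.

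**Formula.** Number the days from the Week -4 visit (day 0), so randomization is day W. For a record ending on day E, the SAP duration is E + g + 1, and the ratio to the correct value is (E + g + 1)/W.

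**Intended case.** The end date is the last dose and Day 1 is the next due date, so E = W − (g + 1). The duration is W and the ratio is 1.00 for every schedule.

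**Record ending k days later than that.** The ratio is (W + k)/W.

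| Situation, W = 28 | k (days) | Ratio |
|---|---|---|
| Every 4 weeks, one week late | 7 | 35/28 = 1.25 |
| Every 4 weeks, half an interval before Day 1 | 14 | 42/28 = 1.50 |
| Three times weekly, ends day before Day 1 | 1.33 | 29.33/28 = 1.05 |
| Weekly, ends day before Day 1 | 6 | 34/28 = 1.21 |
| Every 2 weeks, ends day before Day 1 | 13 | 41/28 = 1.46 |
| Every 4 weeks, ends day before Day 1 | 27 | 55/28 = 1.96 |
| Every 8 weeks, ends day before Day 1 | 55 | 83/28 = 2.96 |

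If screening is extended to 35 days, the 4-weekly extreme is 62/35 = 1.77.

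**Effect on the cut-points.** At a ratio of 1.25, a true ERI of 2.0/1.25 = 1.60 or a true dose of 7,000/1.25 = 5,600 U/week reaches the cut. At 55/28, a true ERI of 1.02, a true 229 U/kg/week or a true 3,564 U/week does.

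**Example** (assumed: darbepoetin 200 µg every 4 weeks, dry weight 70 kg, Hgb 100 g/L).
- Correct dose: 250 × 200 × 0.25 = 12,500 U/week; ERI 12,500/70/100 = 1.79, not a hyporesponder.
- Record one week late: 12,500 × 1.25 = 15,625 U/week; ERI 2.23, a hyporesponder.
- Record ending the day before Day 1: 12,500 × 55/28 = 24,554 U/week; ERI 3.51, a hyporesponder.

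**With the cap at the day before randomization.** Every late-ending case in the table has a duration of 28 of 28 days and a ratio of 1.00. The intended case is unchanged.

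**The case against.** The strongest reply is that the rule works in the situation the trial is designed to produce. Protocol 7.1 has participants stop their ESA so that Day 1 falls, as near as practicable, on the next due date. SAP 14.4.1.5 treats a reported stop date as a day on which the drug was taken, so the end date would be the last dose. End date plus gap factor then lands on the day before Day 1, and the ratio is 1.00. This stands, and it means that the large ratios need a departure from the switch plan or a different way of completing the end date.

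It does not remove the problem. The protocol's alignment is an aim, not a requirement. SAP 14.4.1.5 was written to assign study phases, and the prior ESA derivation does not itself say whether an end date is the last dose or the end of the regimen. SAP 14.7.2.1 also moves partial stop dates to the end of the month or year, which can place an end date after Day 1.

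Two further replies are fair. Iron may continue after Day 1 and its rule provides for ongoing records, so a cap is more obviously needed there than for an ESA that is stopped. The one-time-dose branch caps only for doses before Week -4; a one-time dose during screening gets a fixed 7 days, which counts it once. Neither reply explains why days outside the stated period should enter the numerator.

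A reader might also take inclusion criterion 2, which requires ESA use "continuing during the screening period until randomization (Day 1"), to mean that records usually end at or next to Day 1. The criterion concerns continuing use. It does not fix the date entered in the eCRF.

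**Conclusion.** The line is inconsistent with its own period and denominator and should be corrected. The inflation is nil in the intended case, 1.25 for a 4-weekly record ending one week late, and 1.05 to 2.96 across the schedules in the working table at the extreme. These ratios assume a nominal 28-day window and a single record that began on or before Week -4.

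A reader might infer that prior doses in this trial are generally about doubled, or that hyporesponder status is overstated twofold. The documents do not support either. A ratio near 2 needs a 4-weekly record closed the day before Day 1, and it is not the ceiling of the formula. The documents give neither the mix of dosing schedules nor the eCRF end-date convention, so the number affected is unknown. Hyporesponder status is binary: participants near a cut-point can be misclassified, but the status cannot be inflated.

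The consequence is confined to baseline description and subgroup results. Prior ESA dose is not a covariate in the primary Hgb ANCOVA (SAP 7.1.5.1) or the IV iron ANCOVA (7.2.5.1). The hyporesponder p-values are nominal, and subgroup analyses carry no multiplicity adjustment (5.4.2, 5.5). The same rule applies to both arms. No confirmatory conclusion depends on it.

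**What to change.** In SAP 14.6.2.1, for repeating records, set the stop date to the earliest of three dates: the record end date plus its gap factor; the day before the next sequential prior ESA record starts; and the day before randomization. State that a record still ongoing at randomization ends on the day before randomization. The second limit prevents double counting when a dose or product change falls inside the previous record's gap. The program should apply it only to sequential records, so that regimens recorded in parallel are both still counted. It would also help to state whether the end date means the last dose.

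The cost is one line in the SAP and in the derivation program, made before unblinding. No new data are needed.
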